8.3 Pneumonitis

- For **Grade 2 events**, treat with systemic corticosteroids. When symptoms improve to Grade 1 or less, steroid taper should be started and continued over no less than 4 weeks.
- For **Grade 3-4 events**, immediately treat with intravenous steroids. Administer additional anti-inflammatory measures, as needed.
- Add prophylactic antibiotics for opportunistic infections in the case of prolonged steroid administration.

8.4 Diarrhea/Colitis

Subjects should be carefully monitored for signs and symptoms of enterocolitis (such as diarrhea, abdominal pain, blood or mucus in stool, with or without fever) and of bowel perforation (such as peritoneal signs and ileus).

- All subjects who experience diarrhea/colitis should be advised to drink liberal quantities of clear fluids. If sufficient oral fluid intake is not feasible, fluid and electrolytes should be substituted via IV infusion. For Grade 2 or higher diarrhea, consider GI consultation and endoscopy to confirm or rule out colitis.
- For **Grade 2 diarrhea/colitis** that persists greater than 3 days, administer oral corticosteroids.
- For **Grade 3 or 4 diarrhea/colitis** that persists > 1 week, treat with intravenous steroids followed by high dose oral steroids.
- When symptoms improve to Grade 1 or less, steroid taper should be started and continued over no less than 4 weeks.

8.5 Type 1 diabetes mellitus (if new onset, including diabetic ketoacidosis [DKA]) or \geq Grade 3 Hyperglycemia, if associated with ketosis (ketonuria) or metabolic acidosis (DKA)For **T1DM** or **Grade 3-4 Hyperglycemia**

- Insulin replacement therapy is recommended for Type I diabetes mellitus and for Grade 3-4 hyperglycemia associated with metabolic acidosis or ketonuria.
- Evaluate patients with serum glucose and a metabolic panel, urine ketones, glycosylated hemoglobin, and C-peptide.

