7.71 Acceptable Concomitant Medications

All treatments that the investigator considers necessary for a subject's welfare may be administered at the discretion of the investigator in keeping with the community standards of medical care. All concomitant medication will be recorded on the case report form (CRF) including all prescription, over-the-counter (OTC), herbal supplements, and IV medications and fluids. If changes occur during the trial period, documentation of drug dosage, frequency, route, and date may also be included on the CRF.

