7.72 Prohibited Concomitant Medications

Subjects are prohibited from receiving the following therapies during the Screening and Treatment Phase (including retreatment for post-complete response relapse) of this trial:

- Antineoplastic systemic chemotherapy, biological therapy, immunotherapy, not specified in this protocol

- Investigational agents other than pembrolizumab
- Radiation therapy
 - Note: Radiation therapy to a symptomatic solitary lesion or to the brain may be allowed at the investigator's discretion.
- Live vaccines within 30 days prior to the first dose of trial treatment and while participating in the trial. Examples of live vaccines include, but are not limited to, the following: measles, mumps, rubella, varicella/zoster, yellow fever, rabies, BCG, and typhoid vaccine.
- Systemic glucocorticoids for any purpose other than to modulate symptoms from an event of clinical interest of suspected immunologic etiology. The use of physiologic doses of corticosteroids may be approved after consultation with the Sponsor.

Subjects who, in the assessment by the investigator, require the use of any of the aforementioned treatments for clinical management should be removed from the trial. Subjects may receive other medications that the investigator deems to be medically necessary.

The Exclusion Criteria describes other medications which are prohibited in this trial.

There are no prohibited therapies during event monitoring.

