9.0 Ancillary Treatment/Supportive Care

9.1 Supportive Care Guidelines

Subjects should receive appropriate supportive care measures as deemed necessary by the treating investigator. Suggested supportive care measures for the management of adverse events with potential immunologic etiology are outlined below and in greater detail in section 8.0. Where appropriate, these guidelines include the use of oral or intravenous treatment with corticosteroids as well as additional anti-inflammatory agents if symptoms do not improve with administration of corticosteroids. Note that several courses of steroid tapering may be necessary as symptoms may worsen when the steroid dose is decreased. For each disorder, attempts should be made to rule out other causes such as metastatic disease or bacterial or viral infection, which might require additional supportive care. The treatment guidelines are intended to be applied when the investigator determines the events to be related to pembrolizumab.

All blood products and concomitant medications such as antidiarrheals, analgesics, and/or antiemetics received from the first day of study treatment administration until 30 days after the final dose will be recorded in the medical records.

Note: if after the evaluation the event is determined not to be related, the site investigator is instructed to follow the reporting guidance but does not need to follow the treatment guidance. Refer to the table in section 8.1 for dose modification.

It may be necessary to perform conditional procedures such as bronchoscopy, endoscopy, or skin photography as part of evaluation of the event.

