- 15.191 Pembrolizumab side effects vary greatly from those of traditional chemotherapy and can vary in severity from mild to life threatening. Instruct patients to report any side effects to the study team immediately. Side effects may be immediate or delayed up to months after discontinuation of therapy. Most side effects are reversible with prompt intervention of corticosteroids.
- 15.192 Diarrhea can be seen, however, it is less common than that seen with anti-CTLA-4 agents. However it can be severe, leading to colonic perforation. Instruct patients to report ANY increase in the number of stools and/or change in baseline, blood in the stool, abdominal pain to the study team immediately.
- 15.193 Rash/pruritis/dermatitis is seen. Patients should report any rash to the study team. Treat per section 9.0 and monitor for effectiveness.
- 15.194 Monitor LFT's closely as elevations in these levels could indicate early onset autoimmune hepatitis. Patients should also be instructed to report any jaundice, or right upper quadrant pain to the study team immediately.
- 15.195 Pneumonitis can be seen and may be mild (only seen on imaging) to severe. Patients should be instructed to report any shortness of breath, dyspnea, cough, chest pain, etc. to the study team immediately. Patients reporting these symptoms should have a pulse oximetry checked and consider immediate imaging per the treating physician.
- 15.196 Endocrinopathies (including hypopituitarism, hypothyroidism, hypophysitis, and adrenal insufficiency) are seen with this agent. Patients may present only with the vague sense of fatigue and "not feeling well." Additional symptoms may be that of nausea, sweating and decreased activity tolerance. Instruct patients to report these signs or symptoms immediately and obtain appropriate labs as ordered by the treating physician.
- 15.197 Patients who are started on steroid therapy for any side effects of pembrolizumab toxicity should be instructed to take the steroids as ordered, and not to discontinue abruptly as symptoms may return and be severe. Patients may be on steroid therapy for weeks. Instruct patients to report any increase or change in side effects with any dosage decrease as patients may need a slower taper.
- 15.198 Fatigue is common and may or may not be associated with immune related side effects. Assess patient's fatigue level prior to each cycle of therapy and report any changes to the study team.

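### Section 8.4 makes Grade 3 or 4 diarrhea/colitis wait longer for corticosteroids (more than 1 week) than Grade 2 (more than 3 days)

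*Combined protocol and SAP*

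**What the plan says.** Section 8.4 (Diarrhea/Colitis) has one steroid bullet for Grade 2 and one for Grades 3 and 4.

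- Grade 2: for disease "that persists greater than 3 days, administer oral corticosteroids".
- Grade 3 or 4: for disease "that persists > 1 week, treat with intravenous steroids followed by high dose oral steroids".

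The same section asks for fluids at any grade, and for GI consultation and endoscopy to be considered from Grade 2 upward. The table in section 8.2 holds pembrolizumab for Grade 2-3 diarrhea/colitis and stops it permanently at Grade 4. That row refers to 8.4 and says nothing about when steroids should start.

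Elsewhere, section 8.3 says of Grade 3-4 pneumonitis: "immediately treat with intravenous steroids". The nursing guidelines at 15.191 say: "Most side effects are reversible with prompt intervention of corticosteroids". Section 9.1 states when this guidance applies: "The treatment guidelines are intended to be applied when the investigator determines the events to be related to pembrolizumab".

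**The concern.** The more severe grades get the stronger treatment and also the longer wait for it. One would expect the wait to shorten, or at least not lengthen, as severity rises. The protocol treats severe diarrhea as dangerous: 8.4 tells sites to watch for bowel perforation, and 15.192 names colonic perforation as a possible consequence. A site that follows the bullets as written would start steroids in a Grade 2 patient on day 4 and would have no written instruction to start them in a Grade 3 or 4 patient until day 8.

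This is a patient-management matter. It does not touch the confirmed response rate, the sample size, the significance level or the power. No effect is claimed on the 12-week restart window in 8.2 or on the adverse-event stopping rule in 16.9a.

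**Working it through.** The protocol states no figure to reproduce. The check compares two thresholds and then searches for anything that overrides them.

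**1. The two triggers in 8.4.** Count the first day of symptoms at the given grade as day 1.

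| Grade | Condition | Trigger first met | Treatment |
|---|---|---|---|
| 2 | more than 3 days | day 4 | oral steroids |
| 3 or 4 | more than 1 week (7 days) | day 8 | intravenous, then high-dose oral steroids |

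Gap = 8 − 4 = 4 days (days 4, 5, 6 and 7). Ratio of the waits = 7 / 3 = 2.3.

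**2. Is there an earlier Grade 3-4 trigger elsewhere?** No. The diarrhea/colitis row in 8.2 governs only holding, restarting or stopping pembrolizumab. Section 9.1 gives general principles and no timing for colitis.

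**3. How do the other management sections treat Grade 3-4?** Six direct steroids at that grade.

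| Section | Event | Wait at Grade 3-4 |
|---|---|---|
| 8.3 | Pneumonitis | none (stated as immediate) |
| 8.4 | Diarrhea/colitis | more than 1 week |
| 8.6 | Hypophysitis | none |
| 8.7 | Hyperthyroidism | none |
| 8.8 | Hepatitis | none |
| 8.9a | Renal failure or nephritis | none |

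Only 1 of the 6 sections imposes a wait at Grade 3-4. This comparison is supporting evidence only. Sections 8.3, 8.6, 8.8 and 8.9a have no wait at Grade 2 either, so they do not show how a wait should change with grade. The fault lies between the two bullets of 8.4.

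**4. Could the week be time for work-up?** Section 9.1 does ask investigators to look for other causes, such as infection or metastatic disease. It then applies the treatment guidance once the event is judged related to pembrolizumab. Section 8.4 does not tie the week to any work-up, and a work-up rationale would not explain a shorter wait at Grade 2.

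**5. How many patients?** The documents give no Grade 3-4 rate. Section 15.17 lists colitis at 1% to 10% and diarrhea at 10% or more, with no breakdown by grade. For colitis in 41 patients that is 0.01 × 41 = 0.4 to 0.10 × 41 = 4.1 patients. The number with Grade 3 or 4 disease cannot be derived from this.

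**The case against.** The strongest reply is that section 8 is guidance. Section 9.1 describes these measures as suggestions and says: "Subjects should receive appropriate supportive care measures as deemed necessary by the treating investigator". Section 7.71 adds that treatments considered necessary "may be administered at the discretion of the investigator in keeping with the community standards of medical care". The prohibited list in 7.72 covers "Systemic glucocorticoids for any purpose other than to modulate symptoms from an event of clinical interest of suspected immunologic etiology", so steroids for a suspected immune event are not barred. Nothing in 8.4 forbids starting earlier, and harm would require an investigator to withhold steroids from a sicker patient while giving them to a milder one. This stands as a limit on the consequence. It does not correct the threshold: the bullets are written as instructions, and 9.1 excuses sites from the treatment guidance when an event is judged unrelated, which implies that it is otherwise to be followed.

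A second reply is that the Grade 3 or 4 bullet could be read as escalation, with oral steroids already given from day 4. That would be sensible practice, but the text does not say it.

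A third is that 4 days overstates the gap. This is partly right. The protocol does not define when persistence starts, and a patient who worsens from Grade 2 after day 3 has already met the oral-steroid trigger. Four days is therefore a maximum, for a patient at Grade 3 or 4 from the outset.

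Finally, the right timing for severe colitis is a clinical question that these documents do not settle. That is fair, and it is why the clinicians should confirm the replacement.

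**Conclusion.** The concern holds. As written, 8.4 reverses the steroid trigger by severity, leaving up to 4 days in which Grade 2 disease qualifies and Grade 3 or 4 disease does not. This rests on reading the two bullets literally, counting both from the onset of symptoms at that grade, and assuming that the site starts steroids at the written trigger. Investigator discretion and the undelayed drug hold, fluids and work-up reduce the practical risk. The number of patients affected cannot be estimated. The point should be fixed because it is an unexplained safety instruction in the wrong order and is easy to correct.

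**What to change.** In the Grade 3 or 4 bullet of 8.4, delete the one-week persistence condition and keep the rest. The bullet then carries no wait, as in the Grade 3-4 pneumonitis instruction in 8.3. If the sponsor's clinicians want some wait, it should be no longer than the 3 days used for Grade 2, with the reason stated. They should confirm the exact timing in either case. Send sites a memo with the change.

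The cost is a one-line protocol amendment and the memo, with no added visits, tests or patients.

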8.6 Hypophysitis

- For **Grade 2 events**, treat with corticosteroids. When symptoms improve to Grade 1 or less, steroid taper should be started and continued over no less than 4 weeks. Replacement of appropriate hormones may be required as the steroid dose is tapered.
- For **Grade 3-4 events**, treat with an initial dose of IV corticosteroids followed by oral corticosteroids. When symptoms improve to Grade 1 or less, steroid taper should be started and continued over no less than 4 weeks. Replacement of appropriate hormones may be required as the steroid dose is tapered.

8.7 Hyperthyroidism or Hypothyroidism

Thyroid disorders can occur at any time during treatment. Monitor patients for changes in thyroid function (at the start of treatment, periodically during treatment, and as indicated based on clinical evaluation) and for clinical signs and symptoms of thyroid disorders.

Grade 2 hyperthyroidism events (and **Grade 2-4** hypothyroidism):

- In hyperthyroidism, non-selective beta-blockers (e.g. propranolol) are suggested as initial therapy.
- In hypothyroidism, thyroid hormone replacement therapy, with levothyroxine or liothyronine, is indicated per standard of care. Treatment with pembrolizumab may be continued.

Grade 3-4 hyperthyroidism

- Treat with an initial dose of IV corticosteroid followed by oral corticosteroids. When symptoms improve to Grade 1 or less, steroid taper should be started and continued over no less than 4 weeks. Replacement of appropriate hormones may be required as the steroid dose is tapered.

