8.0 Dosage Modification Based on Adverse Events

8.1 Dose Levels

No dose level adjustments are recommended for any adverse reaction, but the dosing interval may be increased by 1 week if required.

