8.2 Dose Modification

Adverse events (both non-serious and serious) associated with pembrolizumab exposure may represent an immunologic etiology. These adverse events may occur shortly after the first dose or several months after the last dose of treatment. Pembrolizumab must be withheld for drug-related toxicities and severe or life-threatening AEs as per **the table below**.

Dose Modification Guidelines for Drug-Related Adverse Events. Use the NCI Common Terminology Criteria for Adverse Events (CTCAE) v. 4.03

CTCAE System/Organ/Class (SOC)	Adverse Event/Toxicity	Hold Treatment For Grade	Timing for Restarting Treatment	Discontinue Subject
Gastrointestinal disorders	Diarrhea/Colitis (8.4)	2-3	Toxicity resolves to Grade 0-1.	Toxicity does not resolve within 12 weeks of last dose or inability to reduce corticosteroid to 10 mg or less of prednisone or equivalent per day within 12 weeks.
		4	Permanently discontinue	Permanently discontinue
Investigations	Increased AST ALT, or Bilirubin	2	Toxicity resolves to Grade 0-1	Toxicity does not resolve within 12 weeks of last dose.
		3-4	Permanently discontinue (see exception below) ¹	Permanently discontinue
Metabolism and nutrition disorders	Hyperglycemia (8.5)	2-3	Toxicity resolves to Grade 0-1	Toxicity does not resolve within 12 weeks of last dose or inability to reduce corticosteroid to 10 mg or less of prednisone or equivalent per day within 12 weeks.
		4	Permanently discontinue	Permanently discontinue
Endocrine disorders	Hyperthyroidism/ Hypothyroidism (8.7)	3	Toxicity resolves to Grade 0-1	Toxicity does not resolve within 12 weeks of last dose or inability to reduce corticosteroid to 10 mg or less of prednisone or equivalent per day within 12 weeks.
		4	Permanently discontinue	Permanently discontinue
	Other: Hypophysitis (8.6)	2	Withhold	Administer corticosteroids and initiate hormonal replacements as clinically indicated Monitor for signs and symptoms of hypophysitis (including hypopituitarism and adrenal insufficiency)
		3-4	Withhold or permanently discontinue	
General disorders and administration site conditions	Infusion Reaction (8.9)	3-4	Permanently discontinue	Permanently discontinue

CTCAE System/Organ/Class (SOC)	Adverse Event/Toxicity	Hold Treatment For Grade	Timing for Restarting Treatment	Discontinue Subject
Respiratory, thoracic and mediastinal disorders	Pneumonitis (8.3)	2-4	Permanently discontinue	Permanently discontinue

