Renal and urinary disorders	Renal Failure or Nephritis (8.9a)	2	Toxicity resolves to Grade 0-1	Toxicity does not resolve within 12 weeks of last dose or inability to reduce corticosteroid to 10 mg or less of prednisone or equivalent per day within 12 weeks.
		3-4	Permanently discontinue	Permanently discontinue
Cardiac disorders	Myocarditis	1-2	Withhold	Based on severity of the AE administer corticosteroids. Ensure adequate evaluation to confirm etiology and/or exclude other causes
		3-4	Permanently discontinue	Permanently discontinue
	All other immune-related AEs	2	Withhold	Based on type and severity of AE administer corticosteroids Ensure adequate evaluation to confirm etiology and/or exclude other causes
		3	Withhold or discontinue based on the type of event; Events that require discontinuation include and not limited to: Guillain-Barre Syndrome, encephalitis	
			Recurrent grade 3	
		4	Permanently discontinue	
	All Other Drug-Related Toxicity ²	3 (Severe)	Toxicity resolves to Grade 0-1	Toxicity does not resolve within 12 weeks of last dose or inability to reduce corticosteroid to 10 mg or less of prednisone or equivalent per day within 12 weeks.

CTCAE System/Organ/ Class (SOC)	Adverse Event/ Toxicity	Hold Treatment For Grade	Timing for Restarting Treatment	Discontinue Subject
		4	Permanently discontinue	Permanently discontinue
Note: Permanently discontinue for any severe or Grade 3 drug-related AE that recurs or any life-threatening event. ¹ For patients with liver metastasis who begin treatment with Grade 2 AST or ALT, if AST or ALT increases by greater than or equal to 50% relative to baseline therapy should be held up to 3 weeks. If this does not resolve to grade 2, therapy should be discontinued. Steroids can be used to treat elevated AST/ ALT (see section 8.7). Resolution to grade 2 with steroid treatment will be allowed continuation on therapy. ² Patients with intolerable or persistent Grade 2 drug-related AE may hold study medication at physician discretion. Permanently discontinue study drug for persistent Grade 2 adverse reactions for which treatment with study drug has been held, that do not recover to Grade 0-1 within 12 weeks of the last dose.				

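### Hypothyroidism at grade 4, or at unresolved or recurrent grade 3: the Section 8.2 table stops pembrolizumab, but Section 8.7 lets it continue

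*Combined protocol and SAP*

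**What the plan says.** Section 8.2 introduces its dose-modification table in mandatory terms: "Pembrolizumab must be withheld for drug-related toxicities and severe or life-threatening AEs as per" the table. One row, labelled "Hyperthyroidism/ Hypothyroidism (8.7)", covers both thyroid disorders:

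- Grade 3: hold until the event returns to grade 0-1. The patient is discontinued under this condition: "Toxicity does not resolve within 12 weeks of last dose or inability to reduce corticosteroid" to the stated prednisone level within the same period.
- Grade 4: stop permanently.

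The Note under the table adds a general rule: "Permanently discontinue for any severe or Grade 3 drug-related AE that recurs or any life-threatening event". It makes no exception for hypothyroidism.

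Section 8.7, the section that this row cites, opens a block headed "Grade 2 hyperthyroidism events (and Grade 2-4 hypothyroidism)". Within it the instruction is: "In hypothyroidism, thyroid hormone replacement therapy, with levothyroxine or liothyronine, is indicated per standard of care. Treatment with pembrolizumab may be continued". That permission carries no limit by grade, by resolution or by recurrence.

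Section 9.1 describes the status of the event-specific guidance: "Suggested supportive care measures for the management of adverse events with potential immunologic etiology are outlined below and in greater detail in section 8.0". It applies that guidance to events judged related to pembrolizumab, and in a further note it sends the reader to a table in Section 8.1 for dose modification.

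**The concern.** Two current passages give different dosing instructions for the same events. Both apply to events related to the drug: the table by its title, the Section 8.7 guidance by Section 9.1. A reader who goes from the table row to the section it cites finds a permission that the row does not allow.

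In a multicenter trial, sites could therefore apply a patient-safety rule differently, and either reading can cause harm:

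- If the table is what the sponsor intends, a site relying on Section 8.7 doses through an event that requires a stop.
- If Section 8.7 is what the sponsor intends, a site following the table withdraws treatment for an event that was meant to be managed with hormone replacement. Section 1.2 says there is no clearly established therapy after first line. A patient with stable disease or partial response who is stopped this way before 24 months also meets neither route into the Second Course Phase in Section 13.9, which requires a confirmed complete response or stopping after 24 months for reasons other than progression or intolerance.

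**Working it through.** The plan gives no figure to reproduce. The check sets the texts side by side for drug-related hypothyroidism, then sizes the reach.

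| Situation | Section 8.2 table and Note | Section 8.7 | Result |
|---|---|---|---|
| Grade 2 | No hold required by the thyroid row | May continue | Consistent |
| First grade 3, recovered to grade 0-1 | May restart | May continue | Consistent |
| Grade 3, not yet back to grade 0-1 | Hold | May continue | Conflict |
| Grade 3, unresolved 12 weeks after last dose | Discontinue | May continue | Conflict |
| Grade 3, recurrent | Permanent stop (Note) | May continue | Conflict |
| Grade 4 | Permanent stop (row; also the Note if life-threatening) | May continue | Conflict |

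**Can the permission be read as limited to grade 2?** No. Section 8.7 gives hypothyroidism its own range, grades 2 to 4, while it splits hyperthyroidism into grade 2 and grades 3-4.

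**Is it only supportive-care text?** No. It is a statement about dosing. Sections 8.3 to 8.6, 8.8 and 8.9a give management only. Section 8.9b does address dosing, and at grades 3-4 it agrees with the table.

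**Does the table carve out hypothyroidism?** No. Its footnote 1 makes an explicit exception for AST and ALT. There is no similar footnote for the thyroid row.

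**Does any sentence set precedence?** No. The Section 9.1 pointer names Section 8.1, which contains no table, and it sits in a note about events judged not related to treatment.

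**Number of patients.** Inputs: maximum accrual of 41 (Section 16.4), and hypothyroidism listed in Section 15.17 among toxicities at 1% to 10%, with no grade given. Assuming that range is any grade and applies to this population:

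- 41 × 0.01 = 0.41 patients
- 41 × 0.10 = 4.1 patients

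Grade 3-4 is a subset of these, and the documents do not give its share.

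**Doses per affected patient.** Count from the last dose given, at week 0.

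- Ongoing grade 3, 3-week interval: doses fall due at weeks 3, 6, 9 and 12, of which 3 come before the 12-week limit.
- Ongoing grade 3, with the Section 8.1 extension ("the dosing interval may be increased by 1 week if required"): doses fall due at weeks 4, 8 and 12, of which 2 come before the limit.
- The table skips these doses and Section 8.7 permits them. Beyond week 12 the table discontinues while Section 8.7 still permits dosing, so 3 (or 2) is not an upper bound on the total difference.
- Grade 4 or recurrent grade 3: the table or Note allows 0 further doses, while Section 8.7 permits continuation.

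These counts are doses in dispute, not an estimate of doses actually given.

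**The case against.** The strongest reply is that the protocol largely resolves this itself. Section 8.2 uses mandatory language, Section 8.7 only grants a permission, and a permission does not cancel a required stop. Section 9.1 calls the event-specific text suggested measures, and its pointer to Section 8.1 is plausibly a one-digit slip for 8.2. A site that follows the table complies with both texts.

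Much of that stands. A careful site would probably follow the table, which lowers the risk. It does not settle what the sponsor meant: the explicit grade 2-4 range suggests that someone intended continued dosing on hormone replacement, and nothing states that the table overrides Section 8.7.

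The second reply is that reach is tiny. This is also largely right. Assuming, purely for illustration, that 5% to 20% of cases reach grade 3-4, the number is 0.41 × 0.05 ≈ 0.02 to 4.1 × 0.20 ≈ 0.8 patients.

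The third reply is oversight. Thyroid tests are due on Day 1 of each cycle (Section 4.0), dosing follows all assessments (7.4), hypothyroidism is graded at each evaluation (10.52), grade 4 events reach the study team in real time (16.8), and unacceptable adverse experiences require discontinuation (13.5). Late detection is therefore not the worry. But these steps bring the event to attention without saying whether to dose. At grade 3 without hospitalization, Section 10.31 exempts hypothyroidism from expedited reporting, so differing practice might show only in routine forms.

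**Conclusion.** The inconsistency is real and should be fixed. For drug-related hypothyroidism, the Section 8.2 table and Note require pembrolizumab to be held or stopped at grade 4 and at unresolved or recurrent grade 3, where Section 8.7 allows it to continue. The mandatory wording favours the table, but the documents do not show which text is the drafting error.

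The number of patients is unknown and probably small. The 0.41 to 4.1 figure rests on reading Section 15.17 as an any-grade frequency that carries over to this population, and only the grade 3-4 share of it matters. For a patient who is affected, the difference is between holding or ending treatment and continuing it. The sample size and the rule of 7 or more confirmed responses in 35 patients are not affected.

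**What to change.** Give one dosing instruction for each grade of hypothyroidism. The sponsor should choose one of two routes:

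- **If the table is intended:** limit the continuation sentence in Section 8.7 to grade 2, and to a first grade 3 event once it has recovered to grade 0-1.
- **If continuation on hormone replacement is intended:** split the thyroid row so that hypothyroidism follows Section 8.7, and exempt it from the Note on recurrent grade 3 and life-threatening events.

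Either way, state that the Section 8.2 table governs dosing, and change the pointer in Section 9.1 from 8.1 to 8.2.

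The cost is one protocol addendum and a notice to sites. Design, sample size and data collection stay as they are.

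### Section 8.7 permits continued pembrolizumab for Grade 2-4 hypothyroidism, while the 8.2 table requires a hold at grade 3 and a permanent stop at grade 4

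*Combined protocol and SAP*

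**What the plan says.** Section 8.2 introduces its table in mandatory terms: "Pembrolizumab must be withheld for drug-related toxicities and severe or life-threatening AEs as per" the table. One row, "Hyperthyroidism/ Hypothyroidism (8.7"), covers both thyroid disorders. At grade 3 treatment is held until grade 0-1. It ends if that is not reached within 12 weeks of the last dose, or if corticosteroids cannot be reduced to the stated level in that time. At grade 4 treatment ends for good. The Note under the table adds: "Permanently discontinue for any severe or Grade 3 drug-related AE that recurs or any life-threatening event".

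Section 8.7 treats the two disorders separately. Its first block is headed "Grade 2 hyperthyroidism events (and Grade 2-4 hypothyroidism"). The hypothyroidism bullet there calls for thyroid hormone replacement and closes with "Treatment with pembrolizumab may be continued". A second block covers grade 3-4 hyperthyroidism only and says nothing about dosing.

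Section 9.1 tells sites: "Refer to the table in section 8.1 for dose modification". Section 8.1 contains no table. It is a single sentence that begins "No dose level adjustments are recommended for any adverse reaction" and allows the dosing interval to be lengthened by a week.

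**The concern.** A site that follows the row's own reference to 8.7 finds a permission that expressly reaches grade 4, the grade at which the row ends treatment. The main risk is re-dosing after an event that the table and Note say must end treatment. There is a second risk if the sponsor meant 8.7 to govern hypothyroidism. Following the table would then take patients off study drug unintentionally, in a disease for which section 1.2 says nothing is clearly established after first line. Two sites could handle the same patient differently, and each could point to protocol text.

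**Working it through.** No plan figure needs reproducing. The check is a comparison of the texts, grade by grade, for drug-related hypothyroidism.

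| Grade | 8.2 thyroid row and Note | 8.7 hypothyroidism bullet | Result |
|---|---|---|---|
| 2 | No hold in the thyroid row | May continue | Agree |
| 3 | Hold until grade 0-1; permanent stop if it recurs (Note) | May continue | Differ on the plain reading |
| 4 | Permanent stop (row); permanent stop if life-threatening (Note) | May continue | Conflict |

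**Could the texts address different patients?** No. The table concerns drug-related events, and 9.1 says the management guidance applies when the investigator judges the event related to pembrolizumab.

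**Is there an exemption?** Footnote 1 concerns AST/ALT in patients with liver metastases. Footnote 2 concerns intolerable or persistent grade 2 events. Neither reaches grade 3-4 hypothyroidism, and the Note has no exception for it.

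**Is the grade 4 conflict dependent on the Note?** No. The grade 4 line of the row conflicts with 8.7 by itself. The Note adds to it for life-threatening events, which is how the infusion-reaction table in 8.9b describes grade 4.

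**Can grade 3 be reconciled?** Partly. If continued means resumed once the hold is over, the two texts fit for a first grade 3 event. That reading does not cover a recurrence, for which the Note requires a permanent stop.

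**What does the difference amount to at grade 3?** Dosing is every 3 weeks and the table allows up to 12 weeks from the last dose. With a restart at week 12, the doses due at weeks 3, 6 and 9 are missed, so up to 3 doses under the table and none under the plain reading of 8.7.

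**How many patients?** Section 15.17 lists hypothyroidism in its 1%-10% band for all grades together. With the maximum accrual of 41, that is 41 × 0.01 = 0.41 to 41 × 0.10 = 4.1 expected cases. These figures include grades 1 and 2, where there is no conflict, so they do not measure it. The documents give no grade split. As an assumption for scale only, let 2%-20% of cases reach grade 3-4. Then 41 × 0.01 × 0.02 = 0.0082 to 41 × 0.10 × 0.20 = 0.82 patients are expected. Grade 4 alone would be a smaller, unknown part of that.

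**The case against.** The strongest reply is that the documents already steer a site to the table. Section 8.2 is the section on dose modification and says must; 8.7 gives event management and says may. Section 9.1 describes the section 8 event guidance as suggested supportive care and sends the reader to the table for dosing. Its reference to 8.1 is a one-digit slip, since 8.2 holds the only such table. Under 16.8 the study team hears of every grade 4 or 5 event in real time, and the reporting exemption in 10.31 covers hypothyroidism only at grades 1 to 3. A grade 4 case is therefore unlikely to be handled differently without anyone noticing.

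Most of this stands. It makes the table the better reading and lowers the chance that a wrong dose goes unseen. It does not remove the problem. No sentence gives the table precedence, and the row itself refers the reader to 8.7. The bullet is the more specific text and names grade 4. Notification is not a dosing rule, and the real-time notice in 16.8 does not extend to grade 3.

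A reader might infer that the protocol issues two opposite orders that no site can obey together. The documents do not support that: 8.7 grants a permission, and a site that stops complies with both sections. A reader might also infer damage to the trial's result. Nothing in the texts links this wording to the confirmed response rate or to the 7-of-35 rule.

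**Conclusion.** The point holds as a limited dosing-safety inconsistency: a mandatory stop in 8.2 against an unrestricted permission in 8.7. It affects two grades of one adverse event. It is clear at grade 4 and holds at grade 3 on the plain reading. This conclusion rests on the wording alone and needs no assumed rate. The number of patients affected should be small, with fewer than one expected under the assumed 2%-20% share, but the documents cannot confirm that share. The correction is worth making because the permission as written could support re-dosing a patient whom the table removes from treatment, and because it costs almost nothing.

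**What to change.** End the hypothyroidism bullet in 8.7 so that it reads: "Treatment with pembrolizumab may be continued" *at Grade 2; for Grade 3-4 follow the table in 8.2.* In the same edit, change the 9.1 pointer from 8.1 to 8.2.

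If the sponsor instead intends continuation on hormone replacement at grades 3-4, which is a clinical decision, split the thyroid row. Keep the grade 3 hold and grade 4 stop for hyperthyroidism, state the continuation rule for hypothyroidism, and add a matching exception to the Note. Apart from the disputed sentence, the documents offer no support for this second course.

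Until the sponsor decides, sites should follow the table.

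The cost is one sentence and one cross-reference in the next addendum, or, for the alternative, one row split, one clause in the Note and the same cross-reference. Sample size, endpoint and analysis do not change.
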